#### 7.1.1 Solicited injection site reactions

Solicited injection site reactions after IM and/or ID administration are defined as AEs with the following PTs:

- Injection site erythema
- Injection site pruritus
- Injection site pain (covers both the lower level terms *injection site tenderness* and *injection site pain*)
- Injection site swelling
- Injection site warmth

occurring in the period after and up to and including 14 days after Day 0, Day 28, and Day 112 vaccination.

The number and percentage of subjects and the number of events will be presented by PT:

- At Day 0 for the four treatment regimens present

- Cohort A-C
- Cohort D
- Cohort E
- Cohort F
- At Day 28 and Day 112 for the 10 treatment regimens present
  - Cohort A1
  - Cohort A2
  - Cohort B
  - Cohort C
  - Cohort D1
  - Cohort D2
  - Cohort E1
  - Cohort E2
  - Cohort F1
  - Cohort F2

The number and percentage of subjects with events occurring in the period after and up to and including 14 days after the Day 0 vaccination and the corresponding 95% CI will be presented together with a pairwise comparison of number of subjects with events using Fishers exact test for the following:

- Cohort A-C vs Cohort D
- Cohort A-C vs Cohort E
- Cohort A-C vs Cohort F

All information will be listed.

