7.1 Primary objectives

- To evaluate the safety of CTH522-CAF01 administered IM in different doses
- To evaluate the safety of non-adjuvanted CTH522 administered TO or ID simultaneously with CTH522-CAF01 IM
- To evaluate the safety of CTH522-CAF09b administered IM

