7.4 Primary endpoint

- Solicited local injection site reactions after ID and/or IM administration of the vaccines: erythema, pruritus, pain, tenderness, swelling, and warmth
- Solicited local reactions after TO administration of the vaccine: watering eyes, swelling of eyelid, eye redness, and eye discomfort
- Solicited systemic reactions after IM and/or ID administration of the vaccines: oral temperature $> 38.3^{\circ}\text{C}$, chills, myalgia and rash
- Any other adverse events (AEs)

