8.1 Overall trial design

The present trial is a phase I, double-blind, parallel, randomised, and placebo-controlled trial of the chlamydia vaccine, CTH522, in healthy adults. The trial will be conducted at Imperial College Healthcare NHS Trust (ICHT), London, in the UK.

[figure not shown]
It is planned to randomly assign 66 subjects into six cohorts. Cohorts A-D investigate CTH522-CAF01 administered IM in two doses (85 µg and 15 µg). Cohort E investigates CTH522-CAF09b administered IM in one dose (85 µg). Cohort F is the placebo group (Figure 1). The enrolled subjects will complete 12 trial visits (Vs) (Table 3).

All subjects in the active groups (cohort A-E) will receive three IM injections of the adjuvanted CTH522 and some (cohort B and C) will receive the non-adjuvanted CTH522 via the TO or ID route (given at the same time as the 2nd and 3rd IM vaccinations). All active groups will receive TO administration as a boost at Day 140 of either the non-adjuvanted CTH522 (12 µg in each eye) or placebo.

- Cohort A will receive three IM vaccination of 85 µg CTH522-CAF01. This cohort is divided into two groups: A1 will receive ID placebo at Day 28 + Day 112, and TO placebo at Day 140, while A2 will receive TO placebo at Day 28 + Day 112, and non-adjuvanted TO CTH522 boost at Day 140.
- Cohort B will receive three IM vaccinations of 85 µg CTH522-CAF01. This cohort is divided into two groups: B1 will receive TO vaccination of the non-adjuvanted CTH522 at Day 28 and 112 and TO placebo at Day 140, while B2 will receive the same for Day 28 and 112, but non-adjuvanted TO CTH522 boost at Day 140. The two additional TO doses of CTH522 (12 µg in each eye) are administered in each eye. The rationale for this schedule is to investigate the impact of simultaneous TO administration of the antigen on the immunogenicity results.
- Cohort C will receive three IM vaccinations of 85 µg CTH522-CAF01. This cohort is divided into two groups: C1 will receive ID vaccination of the non-adjuvanted 24 µg CTH522 at Day 28 and 112 and TO placebo at Day 140, while C2 will receive the same for Day 28 and 112, but TO 12 µg CTH522 boost in each eye at Day 140. The rationale for this schedule is to investigate the impact of simultaneous ID administration of the antigen on the immunogenicity results.
- Cohort D will receive three IM vaccinations of 15 µg CTH522-CAF01. The rationale for the A and D cohorts is to investigate the impact of the two IM CTH522 doses on the immunogenicity results.

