9.2.2 Treatment administered

The randomised subjects will be vaccinated with the IMPs (non-adjuvanted CTH522) and reconstituted IMPs (adjuvanted CTH522) accordingly to the schedule and route specified in Figure 1. On-site reconstitution of the adjuvanted IMPs is performed by mixing the CTH522 with CAF01 or CAF09b. Specific instruction of the on-site reconstitution can be found in the Vaccine Management Manual, which is prepared by SSI.

The preferred location for IM and ID administrations is into (IM) or into the skin overlying (ID) the non-dominant deltoid muscle. Each IM administration will consist of 85 µg CTH522-CAF01, 15 µg CTH522-CAF01 or 85 µg CTH522-CAF09b in a volume of 0.5 ml per injection. Each ID administration will consist of 24 µg CTH522 in a volume of 0.1 ml per injection. The IM and ID injections must be administered within five minutes of each other and approximately 2 cm apart from each other. As long as the two injections are administered within five minutes, it does not matter which one (IM or ID) is given first. The IM injection will be performed with a 1–2 ml polypropylene syringe via a 23–25-gauge needle. The ID injection will be with a 1 ml syringe via a microneedle device.

The TO administration in both eyes will consist of 24 µg CTH522 (non-adjuvanted) in a volume of 0.04 ml; thus, each eye is administered 12 µg of CTH522 TO in a 0.02 ml drop. The eye drops should be given five minutes apart, with the right side first to follow by the left side. The TO administrations will be performed using a Gilson MICROMAN positive displacement pipette, which will be provided by ICL.

Each colour coded vial and cardboard box of IMPs is labelled with the content of the vial as described in the Vaccine Management Manual. The identity of the injected trial vaccine will be known to the clinical site staff administering the trial vaccine and by the unblinded trial monitor. However, the identity of the trial vaccine administered will remain unknown to the subject during the trial.

The IMPs should only be administered by authorised staff as indicated in the investigational site signature and delegation form.

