12.1 Risks and benefits

At present, there is only data available for CTH522 with or without the adjuvants CAF01 or Al(OH)₃ from a completed clinical trial that included 35 adult female volunteers [9]. From this trial, safety data where CTH522-CAF01 have been administered IM are known. The related AEs (> one in ten subjects) after IM administration of CTH522-CAF01 reported were:

- injection site pain, injection site tenderness and injection site movement impairment after IM vaccination
- sneezing, nasal congestion and rhinorrhoea after intranasal vaccination
- systemic reactions after IM or IN vaccination were headache, fatigue, malaise and myalgia

The most frequently reported treatment-emergent AEs were headache, oropharyngeal pain, and dysmenorrhoea. Please refer to the IB for more information.

Based on general considerations, experience from clinical trials with CAF01, CAF09b and CTH522, the IMPs to be used in the present trial are expected to be safe.

Anaphylactic reactions are very rare. However, appropriate medical treatment and trained staff will be available in case an anaphylactic reaction occurs.

Vasovagal syncope (i.e. fainting), may occur. It will be attempted to minimise the occurrence of this reaction, by allowing the subjects to lie down during the administration of vaccine and blood drawings.

The trial personnel performing the procedures will inform the subjects on the procedures before blood drawings and administration of vaccine, and it will be emphasised to the subject, that participation is voluntary and that he/she at any time can withdraw from the trial.

This is a healthy volunteer trial, so there will be no direct health benefit to the individual subject. However, they will undergo general health and sexually transmitted infection screening. Sexually transmitted infection may be asymptomatic, and if diagnosed, the subjects will be counselled and offered referral to the confidential service provided by their local NHS genitourinary medicine clinic. If trial results are satisfactory, further clinical trials will be initiated and may lead to a marketed vaccine against trachoma and/or genital chlamydia.

The subjects will receive payment to compensate them for their time, inconvenience, travel expenses, etc. They will be paid £100 per scheduled clinic visit, to a maximum of £1200, paid as a lump sum at the end of participation. Volunteers who attend screening but who are not enrolled will not receive payment.

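### SAP 7.1.1 merges IM-site and ID-site reactions and formally compares cohorts only at Day 0, so local reactions to ID CTH522 get no site-specific summary and no comparison in the SAP

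*SAP*

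**What the plan says.** Protocol 7.1 makes this a primary objective: "To evaluate the safety of non-adjuvanted CTH522 administered TO or ID simultaneously with CTH522-CAF01 IM". The matching endpoint in Protocol 7.4 pools the two routes: "Solicited local injection site reactions after ID and/or IM administration of the vaccines: erythema, pruritus, pain, tenderness, swelling, and warmth". Protocol 10.1.1 and 11.4.4 pool them as well.

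SAP 7.1.1 follows the protocol: "Solicited injection site reactions after IM and/or ID administration are defined as AEs with the following PTs". Five PTs follow, and injection site pain also takes in tenderness. For each regimen, "The number and percentage of subjects and the number of events will be presented by PT". At Day 28 and Day 112 the columns include Cohort C (ID CTH522) and Cohort A1. A1 has the same IM product and dose as C but saline by the ID route: "A1 will receive ID placebo at Day 28 + Day 112, and TO placebo at Day 140". No row or column identifies the injection site.

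On administration, Protocol 9.2.2 states: "The IM and ID injections must be administered within five minutes of each other and approximately 2 cm apart from each other".

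The Fisher tests in SAP 7.1.1 cover the period after the Day 0 vaccination only (Cohorts A-C vs D, E and F). No ID dose has been given by then. For the TO route, SAP 7.1.2 plans 95% CIs and Fisher tests of Cohort B vs A2 and B vs F1 at both Day 28 and Day 112.

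**The concern.** The objective names TO and ID together, but the SAP treats them differently. Ocular PTs identify their own site, and the TO antigen is compared with its saline control on the same IM product. ID reactions share their PTs with IM reactions, and no ID comparison is planned.

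A subject who already counts for a PT because of the IM injection adds nothing to the percentage by also reacting at the ID site. If the IM injection often causes that reaction, Cohort C can look close to A1 even when the ID antigen itself often causes it. What is at stake is whether the report can say how locally reactogenic ID CTH522 is, which is part of what the trial sets out to learn.

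**Working it through.** The documents give no sample size calculation, power or reaction rate for this endpoint, so there is no figure to reproduce. The check has three parts.

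**1. What is known about the IM rate.** Protocol 12.1 lists related events seen in more than one in ten subjects after CTH522-CAF01 IM in the earlier trial. The local terms are "injection site pain, injection site tenderness and injection site movement impairment after IM vaccination". Of these, pain and tenderness are solicited here, and both fall under the PT injection site pain. Erythema, pruritus, swelling and warmth are not on the list. I take that to mean an IM rate of at most 10% for those four; this is an inference. The pain rate is not given beyond being above 10%.

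**2. How much the merged percentage hides.** Let p_IM and p_ID be the per-subject probabilities of a given PT at each site.

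- Merged rate, sites independent: 1 − (1 − p_IM)(1 − p_ID)
- Excess due to the ID dose: p_ID(1 − p_IM)
- Share of ID reactors hidden: p_IM

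If the same subjects tend to react at both sites, the hidden share is larger than p_IM.

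Assume p_ID = 60% with CTH522 and 0% with saline, a true ID-site difference of 60 points:

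| Assumed IM rate | Merged, C | Merged, A1 | Visible difference | Hidden share |
|---|---|---|---|---|
| 10% | 1 − 0.9 × 0.4 = 64% | 10% | 54 points | 10% |
| 50% | 1 − 0.5 × 0.4 = 80% | 50% | 30 points | 50% |
| 70% | 1 − 0.3 × 0.4 = 88% | 70% | 18 points | 70% |
| 90% | 1 − 0.1 × 0.4 = 96% | 90% | 6 points | 90% |

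The four unlisted PTs belong at or below the first row. Injection site pain could be anywhere from just above the first row to the last.

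**3. What a comparison could detect.** Group sizes are only in Figure 1, which is not shown, so I assume 12 in Cohort C and 6 in A1. I also assume an ID rate of 80% with CTH522 and 10% with saline. Exact two-sided Fisher power at 5% is:

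- ID site only: 83%
- Merged sites: 70%, 28%, 12% and 1% at IM rates of 10, 50, 70 and 90%

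From 10/5 to 16/8 subjects, the ID-site figure runs from 70% to 93%. The merged figure runs from 55% to 84% at an IM rate of 10%, and from 8% to 20% at 70%. With an ID rate of 50%, power at 12/6 is only 23% even by site.

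**The case against.** Several points on the other side are sound.

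- **Events are counted as well as subjects.** A second reaction can add an event. But events carry no site either, and because pain and tenderness share a PT, two events may be two terms at one site, two episodes or two sites. This is a partial answer only.
- **A1 stands beside Cohort C.** The added effect of ID antigen can be read from those columns. A reader might infer that merging hides any difference between ID CTH522 and ID saline. The table above shows otherwise: the difference is attenuated, not removed.
- **The objective concerns ID given simultaneously with IM.** A reader might call the merged endpoint biased towards finding no added reactogenicity. The documents do not support that. Whether adding ID antigen changes how many subjects have a local reaction is a fair regimen-level question, and merged C vs A1 answers it directly. Site-specific reactogenicity is a further question that is left unanswered.
- **The protocol provides more widely for testing.** Protocol 11.4.4 foresees Fisher tests of active groups against placebo and against each other, with no time point. That would cover C vs A1, but SAP 7.1.1 restricts the tests to Day 0. SAP 8 says only in general terms that analyses were adapted to the data.
- **Site may be hard to assign.** The protocol's toxicity scale starts Grade 1 erythema and swelling at 2.5 cm. Two circular areas of that size have radii of 1.25 cm; these add to 2.5 cm, so areas centred 2 cm apart overlap. Subjects would also have to localise pain across that gap. This stands, and it limits what a site split can yield.
- **Site may already be recorded, or it may be too late to record it.** The diary and eCRF are not among the documents, and the planned listing of all information may include site. SAP 4 says that all randomised subjects have observed data, so a new diary field could not recover past reactions. This also stands.

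**Conclusion.** The gap is real, but narrower than general masking of local reactions. SAP 7.1.1 gives ID CTH522 no site-specific summary and no comparison after any ID dose, although its safety is part of a primary objective and the TO route gets both. No other text in the documents fills the gap.

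Material masking is plausible for one PT of the five, injection site pain. Its size depends on an IM rate known only to exceed 10%. Under independence, an assumed 60-point difference would show as 54 points at an IM rate of 10%, falling to 6 points at 90%. For erythema, pruritus, swelling and warmth, about 10% or less of ID reactors would be hidden if absence from the earlier trial's list means a rate of at most 10%. For these the problem is mainly that a reaction in Cohort C cannot be assigned to a site. All reaction rates and group sizes used here are assumptions. The point is a cheap improvement to the presentation and analysis, not a flaw that invalidates the endpoint.

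**What to change.** In SAP 7.1.1:

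1. Add a Cohort C vs A1 contrast with 95% CI at Day 28 and at Day 112, to match the TO contrast in SAP 7.1.2. Both cohorts receive the same IM product and differ in ID CTH522 vs ID saline.
2. State whether the diary or eCRF records the site of a local reaction.
3. If it does, add descriptive rows for IM site, ID site and cannot be separated to the Day 28 and Day 112 tables for A1, C, D2, E2 and F2. Show the site in the listing. Keep the merged row as the endpoint the protocol defines.
4. If it does not, state this as a limitation on any conclusion about ID reactogenicity.

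The change should be made before unblinding. It costs one contrast at two visits and a few table rows, with no new data collection. The downside is limited yield: with 66 subjects in 12 groups and injections "approximately 2 cm apart from each other", many reactions may be unattributable, and the output will be mainly descriptive. The added contrast should fall under the caution on multiple tests already in SAP 7.7.

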11.4.4 Safety analysis

The binary primary endpoints are:

- Solicited injection site reactions after IM and ID administration with the following PTs: injection site erythema, injection site pruritus, injection site pain, injection site swelling and injection site warmth
- Solicited ocular reactions after TO administration with the following PTs: lacrimation increased, swelling of eyelid, ocular hyperaemia and ocular discomfort

- Solicited systemic reactions after vaccination with the following PTs: body temperature increased, chills, myalgia and rash

The frequencies of the binary endpoints will be presented with the corresponding 95% CI.

These endpoints will be analysed by pairwise comparison of active treatment groups versus placebo in 2 x 2 tables (presenting number and percentage of subjects experiencing the criteria) using Fishers exact test. Also, active treatment groups will be compared similarly.

Adverse drug reaction will be presented descriptively by treatment group (number of subjects, percentage of subjects experiencing the event and number of events), in tables of system organ class and PTs in summary tables presenting each group in separate columns.

Vital signs are presented descriptively by treatment group and visit. Both absolute values and changes from baseline are presented both in tables and in box-plots by visit.

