#### 5.1 Statistical Considerations

Baseline is defined as the last assessment with available data prior to the first administration of trial medication. Day 0 is the day of first administration with IMP. Assessments from scheduled visits will be presented when available, otherwise the first unscheduled visit succeeding the scheduled visit in question is used.

Categorical data will be summarized by treatment group, using number and percentages of subjects. For calculation of percentages the denominator will either be the number of subjects in the analysis set or the number of subjects in the analysis set with non-missing values. Continuous data will be presented using the number of subjects (n), mean, standard deviation (SD), median, minimum, and maximum if nothing else is stated. Both the absolute values and the change from baseline will be presented.

Descriptive statistics for all endpoints will be presented by treatment group and visit (if applicable) using observed cases, i.e., no imputation of missing data will be performed.

All statistical tests will be two-sided and performed on a 5 % significance level. Estimated treatment differences and 95 % confidence intervals (CI) will be presented together with the corresponding p-value.

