## 7 Statistical Methodology for Primary and Secondary Endpoints

### 7.1 Analysis and Presentation of the co-Primary Safety Endpoints

The co-primary endpoints are:

- Solicited local injection site reactions after ID and/or IM administration of the vaccines: erythema, pruritus, pain, tenderness, swelling, and warmth occurring up to and including 14 days after any IMP administration
- Solicited local reactions after TO administration of the vaccine: watering eyes, swelling of eyelid, eye redness, and eye discomfort occurring up to and including 14 days after any IMP administration
- Solicited systemic reactions after IM and/or ID administration of the vaccines: oral temperature  $> 38.3^{\circ}\text{C}$ , chills, myalgia, and rash occurring up to and including 14 days after any IMP administration
- Any other adverse events (AEs)

These are collected in the subjects' diaries.

The primary analyses will be carried out for the SAF.

AEs will be coded using the Medical Dictionary for Regulatory Activities (MedDRA) version 22.1 - Sep 2019. AEs will be regarded as treatment emergent AEs (TEAEs) if they occur after administration of randomised treatment.

Only TEAEs will be summarised. The summaries will include number of events, number of subjects, and proportion of subjects reporting these events.

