### 7.1.2 Solicited ocular reactions

[figure not shown]
Solicited local reactions after TO administration are defined as AEs with the following PTs:

- Lacrimation increased
- Swelling of eyelid
- Ocular hyperaemia
- Ocular discomfort

occurring in the period after and up to and including 14 days after Day 28, Day 112, and Day 140 vaccinations.

The number and percentage of subjects and the number of events will be presented by PT:

- At Day 28 and Day 112 for the five TO treatment regimens
  - Cohort A2
  - Cohort B
  - Cohort D1

- Cohort E1
- Cohort F1
- At Day 140 for the 11 TO treatment regimens present, where the placebo cohort (F) will be regarded as one
  - Cohort A1
  - Cohort A2
  - Cohort B1
  - Cohort B2
  - Cohort C1
  - Cohort C2
  - Cohort D1
  - Cohort D2
  - Cohort E1
  - Cohort E2
  - Cohort F

The number and percentage of subjects with events occurring in the period after and up to and including 14 days after the Day 28 and the Day 112 vaccinations and the corresponding 95% CI will be presented by visit together with a pairwise comparison of number of subjects with events using Fishers exact test for the following:

- Cohort B vs Cohort A2
- Cohort B vs Cohort F1

All information will be listed.

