### 7.1.3 Solicited systemic reactions

[figure not shown]
Solicited systemic reactions after IM and/or ID administration are defined as AEs with the following PTs:

- Pyrexia
- Chills
- Myalgia
- Rash

occurring in the period after and up to and including 14 days after the Day 0, Day 28, and Day 112.

*Pyrexia* should be used as PT for temperatures above 38.3°C only, which is not as in the FDA guidelines presented in the protocol Appendix 1 stating temperatures above 38.0°C. For increased temperatures at or below 38.3°C, the PT *Body temperature increased* is used and thus not included as events. If the temperature is unknown, *Pyrexia* will be used, and the event included.

The number and percentage of subjects and the number of events will be presented by PT:

- At Day 0 for the four treatment regimens present
  - Cohort A-C
  - Cohort D
  - Cohort E
  - Cohort F
- At Day 28 and Day 112 for the 10 treatment regimens present
  - Cohort A1
  - Cohort A2
  - Cohort B
  - Cohort C
  - Cohort D1
  - Cohort D2
  - Cohort E1
  - Cohort E2
  - Cohort F1
  - Cohort F2

The number and percentage of subjects with events occurring in the period after and up to and including 14 days after the Day 0 vaccination and the corresponding 95% CI will be presented together with a pairwise comparison of number of subjects with events using Fishers exact test for the following:

- Cohort A-C vs Cohort D
- Cohort A-C vs Cohort E
- Cohort A-C vs Cohort F

All information will be listed.

[figure not shown]

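### For injection-site and systemic reactions the SAP drops the placebo comparisons for CAF09b and low-dose CAF01, and all 95% CIs after Days 28 and 112, without declaring it

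*SAP*

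**What the plan says.** Protocol 11.4.4 lists solicited injection-site, ocular and systemic reactions as binary primary endpoints and makes three commitments:

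- On intervals: "The frequencies of the binary endpoints will be presented with the corresponding 95% CI".
- On tests against placebo, by Fisher's exact test: "These endpoints will be analysed by pairwise comparison of active treatment groups versus placebo in 2 x 2 tables".
- On tests between vaccine arms: "Also, active treatment groups will be compared similarly".

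None of these is tied to a particular dose or cohort.

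SAP 7.1 defines the solicited endpoints as "occurring up to and including 14 days after any IMP administration". SAP 7.1.1 and 7.1.3 then specify, for injection-site and systemic reactions:

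- **Day 0:** counts and percentages for A-C, D, E and F. The interval and the Fisher test are planned for this window only: "14 days after the Day 0 vaccination and the corresponding 95% CI will be presented together with a pairwise comparison of number of subjects". The contrasts are A-C v D, A-C v E and "Cohort A-C vs Cohort F".
- **Days 28 and 112:** counts, percentages and event numbers by preferred term for ten regimens, with no interval and no test.

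For ocular reactions, SAP 7.1.2 does give intervals and tests at Days 28 and 112, including "Cohort B vs Cohort F1".

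SAP 5.1 adds the general rule "Estimated treatment differences and 95 % confidence intervals (CI) will be presented together with the corresponding p-value". SAP section 2 says that departures from the protocol analysis are highlighted in section 8. Section 8 lists the 14-day window, the pyrexia coding rule, the added Wilcoxon tests, and a general line that presentations and analyses are adapted to the nature of the data.

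**The concern.** The three primary objectives are the safety of CAF01 at different doses, of TO or ID antigen given alongside CAF01, and of CAF09b. For injection-site and systemic reactions, the contrasts that address parts of each are missing.

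- **CAF09b (objective 3).** Protocol section 12 says this antigen with CAF09b has not been given to humans before. Its only planned contrast is with CAF01, another active adjuvant. A null A-C v E result does not show how far reactions on CAF09b exceed those on saline.
- **Low dose (part of objective 1).** Cohort D is likewise compared only with the higher dose.
- **ID antigen (part of objective 2).** ID dosing starts on Day 28. Cohort C enters a formal analysis only as part of the pooled Day 0 group, before any ID dose.

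Because SAP 5.1 attaches the estimated difference and its CI to a p-value, a contrast that is not tested also gets no estimated difference. At the later doses, percentages from very small groups would be reported without any statement of precision.

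**Working it through.** **1. Count what the protocol rule implies and what the SAP lists.** Day 0 has four regimens (A-C, D, E, F), so there are C(4,2) = 6 pairs per endpoint: 3 active v placebo and 3 active v active. The SAP lists 3. Missing are D v F, E v F and D v E, so 1 of 3 placebo contrasts survives. At Days 28 and 112, with F pooled, there are 8 active regimens and so 8 placebo contrasts per visit. The SAP lists 0 contrasts and 0 intervals for these two endpoints.

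**2. Group sizes.** Cohort sizes are in a figure not reproduced in the text. Protocol 11.4.3 gives 91% active and 9% placebo out of 66. Only 6 placebo subjects round to 9% (6/66 = 9.1%) and only 60 active subjects round to 91% (60/66 = 90.9%), so the stated split is reproduced. Equal allocation, 60/5 = 12 per active cohort, is an assumption, as are half-cohorts of 6 (3 in placebo). Reaction rates are not given, so a range is used.

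**3. Power of D v F or E v F.** Power is the sum, over all tables with two-sided Fisher p ≤ 0.05, of Bin(a; 12, p₁) × Bin(b; 6, p₀).

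| Placebo rate | Active 50% | 70% | 80% | 90% |
|---|---|---|---|---|
| 10% | 23% | 65% | 83% | 95% |
| 20% | 13% | 45% | 64% | 83% |
| 30% | 7% | 28% | 46% | 68% |

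Sensitivity to cohort size, at 80% v 20% with 6 on placebo: 49% (n = 8), 62% (n = 10), 64% (n = 12), 69% (n = 15).

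**4. Smallest significant results (12 v 6).**

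- 7/12 v 0/6: p = [C(12,7)·C(6,0) + C(12,2)·C(6,5) + C(12,1)·C(6,6)] / C(18,7) = (792 + 396 + 12)/31,824 = 0.038.
- 9/12 v 1/6: p = 0.043.
- 11/12 v 2/6: p = 0.022.

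**5. What an interval would show.** For 9/12 v 1/6 the difference is 0.750 − 0.167 = 58 points, with an exact unconditional score 95% CI of about 8 to 85. Inverting two one-sided exact tests gives about 6 to 88, so the method should be named.

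**6. The retained contrast.** A-C v E (36 v 12) has 12% power at 90% v 80%.

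**7. ID antigen.** C and A1 get the same IM dose and both get an ID injection, antigen in C and placebo in A1. At 12 v 6, power is 1.6% at 100% v 90% and 10% at 100% v 80%, so a test is of little use. As an estimate, 12/12 v 5/6 gives 100 − 83 = 17 points, CI about −12 to 58.

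**8. Later-dose precision (Clopper-Pearson).** 0/3 (F1 or F2) has an upper limit of 1 − 0.025^(1/3) = 71%. 1/6 (for example E1) has limits 0.4% to 64%. 0/12 has an upper limit of 26%.

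**The case against.** The strongest reply is that this is an unpowered phase I trial whose objectives are to evaluate safety, not to test it. Counts for every regimen after each dose are planned, with severity and relatedness tables and full listings, so a reader could compute the missing intervals. SAP 7.7 already urges care with all tests, and no decision rule depends on these. That limits the consequence. It does not explain why the protocol's comparisons were removed, and small groups are a reason to give intervals. The SAP itself tests ocular reactions at Days 28 and 112, against half the placebo cohort.

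Three narrower points are fair:

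- A-C, D, E and F each get a 95% CI on their own Day 0 percentage. What is missing at Day 0 is the D-F and E-F difference with its interval and test.
- The protocol names no visits, so an interval per regimen at Days 28 and 112 is a natural reading of 11.4.4, not an express promise. The omission of D and E against placebo is the firmer conflict.
- Section 8 has its general line about adapting analyses. It identifies no dropped comparison, whereas the added Wilcoxon tests are named.

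C v A1 is at most implied by the protocol and would be imprecise, which is why it is proposed without a test.

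**Conclusion.** The concern holds. For injection-site and systemic reactions, D v F and E v F are not planned, and nothing after Days 28 and 112 has an interval or a contrast. Section 8 does not name this narrowing of protocol 11.4.4. These facts come from the text and do not depend on cohort size.

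The size of the loss does depend on assumptions (12 per active cohort, 6 placebo, the rates shown). The missing placebo tests would be informative if reactions are common on vaccine and rare on placebo (83% power at 80% v 10%) and weak otherwise (7% at 50% v 30%). In the weak cases the difference with its interval is the useful result. The change should be made, but the trial does not stand or fall on it.

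**What to change.** 1. In SAP 7.1.1 and 7.1.3, add D v F and E v F at Day 0, each with the Fisher p-value, risk difference and exact 95% CI. Name the CI method.
2. At Days 28 and 112, add an exact 95% CI for each regimen already tabulated. Add the C v A1 risk difference with exact 95% CI, labelled as an estimate without a test and noted as imprecise if IM reactions are already frequent. Keep F1 and F2 separate for injection-site reactions, since only F2 receives an ID injection.
3. State whether the Fisher tests use any reaction within the endpoint or each preferred term.
4. In section 8, name each protocol 11.4.4 comparison still omitted (D v E, for example) with the reason.

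**Cost:** SAP wording and output on data already collected. With one any-reaction test per endpoint, 2 contrasts × 2 endpoints = 4 tests join the present 3 × 2 = 6, making 10. If run by preferred term (5 + 4 = 9 terms), 18 join 27. All are unadjusted, under the existing SAP 7.7 caution, and intervals in groups of 3 to 12 will be wide.
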